*(Please submit the application in English)***Hong Kong Baptist University**Faculty Research Grant *Category II*

Application Form

(Funding Limit: \$150,000)

1. Project Title:

The Effectiveness of an E-Intervention on Health Behavior Promotion in Chinese University Students

2. Name(s) of Applicant(s):

	Name	Department & Post Title	HKBU Staff I.D. No.
Principal Investigator: (with title e.g. Prof., Dr., Ms., Miss)	[name] ([name])	Assistant [name]	118411
Co-investigator(s): (with title e.g. Prof., Dr., Ms., Miss)	[name]	Associate [name] of Physical Education Nantong University	
	[name]	Associate [name] Section Wuhan University	
	[name]	Associate [name] Section Wuhan University	

	[name]	[name] on Lifelong Learning and Institutional Development Jacobs University Bremen	
--	-------------------	--	--

3. Abstract of research:

(Please provide a short abstract of ½ page or 200 words. The abstract should be comprehensible to a non-specialist)

Through internet and mobile phone SMS technology, and by using the Health Action Process Approach model as a theoretical backdrop, this 8-week theory-based intervention study aims at developing a healthy lifestyle by supporting physical activity (PA) and a healthy dietary for Chinese university students.

Students will be recruited at general PE classes. The online registration and personal information will be completed within the first two weeks of one semester (T0). Then students will be randomly assigned into one of three groups. (1) Intervention group I (IG-I): sequentially with PA first (4 weeks) followed by diet (4 weeks); (2) IG-II: sequentially diet first (4 weeks) and then PA (4 weeks); (3) the control group (CG) will not participate in any support program during the intervention period and the 1-month extension. Besides, all groups will be contacted to collect data at the beginning of the intervention (T1), at the end of intervention (T2), and at one month after the intervention (T3). Data collection will be completed on the e-health learning website through electronic questionnaires.

We will examine whether the students in the two intervention groups improve their motivation for PA and healthy diets in comparison to the control group; whether, with the help of an intervention program, students are able to increase their PA levels and healthy diet consumption, and whether there are different effects between the two intervention programs. We believe the study findings will provide an e-health learning approach to support Chinese university students to maintain their health behavior in daily life.

4. The project aims, its long-term significance:

(State the aims, identify the key issues and problems being addressed and list the possible outcomes of the research project, as well as its significance and value) (Maximum 600 words or 1 page)

Key issues and problems:

A successful transition from late adolescence to adulthood is essential for university students. Physical activity and healthy diet can support this process and lead to positive health outcomes. However, considerable evidence has revealed a significant decline in PA behavior participation among university students worldwide (Vankim, Laska, Ehlinger, Lust & Story, 2010). Additionally, study in China revealed that approximately half of the university students do not eat fruits every day and one third of students do not eat dark vegetables for long time (Li, 2014). Such a pattern of unhealthy lifestyle habit, which is reinforced during university, has a significant effect on behavior and health in later adulthood (Epton, Norman, Dadzie et al., 2014). Therefore, it is critical for university students to be motivated to adopt and maintain healthy lifestyle during this transition period.

The project aims:

The aim of this project is to examine the effectiveness of two website & SMS prompts-based e-health learning courses (intervention groups I-II, IG-I: sequential first physical activity, then dietary; IG-II: sequential first dietary, then physical activity) compared to a control group condition. Individuals who participate in e-health learning programs should be encouraged to develop a healthy lifestyle in their daily life, with a primary focus being on motivation, behaviour change and quality of life.

The possible outcomes of the research project are to provide knowledge on:

1. Participants in the intervention groups (IGs) gain a higher motivation for physical activity and healthy diet in comparison with a control group.
2. Participants in the intervention groups (IGs) increase their physical activity levels and healthy diet consumption in comparison with a control group.
3. Participants in the intervention groups (IGs) gain higher perceived quality of life in comparison with a control group.
4. The order of the addressed behavior (IG-I, IG-II) results in different effects.

Long-term significance:

This study will be the first step in an e-health learning intervention for physical activity and dietary behaviour change in Chinese university students. By using innovative theory-based e-health learning technology, new insights for health education can be gained. In the long term, this study's results will provide information on the usability of e-health learning interventions among university students to develop and support their healthy lifestyle habit in daily life.

In addition, this study will apply the Health Action Process Approach (HAPA; Schwarzer, 2008) model, which has been proved to be applicable to diverse participants in different health behaviours, so that contributions can be made to the development of the HAPA model in health behaviour research among Chinese university students.

To our knowledge, very few studies have provided a direct test of the difference between sequential e-health learning programs for changing multiple health behaviors (e.g., Vandelandotte, De Bourdeaudhuij, Sallis, Spittaels, & Brug, 2005). This study will explore whether the order of the sequential programs (IG-I, IG-II) results in different effects.

5. Objectives (State the objectives in point form):

- Objective 1:** 1. To test whether participants in the intervention groups (IGs) improve their motivation for physical activity and healthy diets compared to the control group.
- Objective 2:** 2. To test whether participants in the intervention groups (IGs) increase their physical activity levels and healthy diet consumption compared to the control group.
- Objective 3:** 3. To test whether the intervention program can improve participants' perceived quality of life.
- Objective 4:** 4. To test whether the order of the addressed behaviours (IG-I, IG-II) results in different effects.

6. Background of research, research plan and methodology: : (Maximum 6 pages, excluding references)

[Summary of related work that has already been done and an outline of previous and alternative approaches to the problem -

(a) By others (give key references)

(b) By the investigator(s) (give key references)

(c) Progress report (for on-going projects)]

[Explain, in terms of the educated layman, the novel idea which you will be introducing to tackle the problem in question. Please include key references. Attach a draft questionnaire should the research plan involve a survey/interview.]

Background of research

(a) Work done by other researchers (with key references)

This intervention study will be based on the Health Action Process Approach (HAPA; Schwarzer, 2008; Figure 1). The basic idea of this approach is that during the process of health behaviour change, people go through different phases in which their thoughts, feelings, and behaviours differ on each level. The HAPA Model distinguishes between motivational processes, in which the intention (goal setting) is the main focus, and volitional processes, in which the initiation and the maintenance (goal pursuit) of the behaviour are central. Within the volitional phase, a distinction between people who have the intention to perform a specific behaviour but do not act (intenders) and people who already perform the behaviour (actors) can be made.

This distinction allows the tailoring of interventions to the variables which are relevant in a specific stage. For example, people who have not formed the intention to change their behaviour (non-intender) benefit most from interventions which increase their risk perception, increase self-efficacy, and promote positive attitudes (e.g., Schwarzer, Cao, & Lippke, 2010). On the other hand, people who already have the intention to change their behaviour, benefit the most from planning interventions (Lippke, Schwarzer, Ziegelmann, Scholz, & Schüz, 2010); such intervention should help them to set goals, determine priorities, and to translate their action plans into behaviour. For people who are currently active, self-regulatory skills are substantial for their maintenance process. The behaviour will mainly be directed by self-efficacy, because it regulates how effort is invested and how persistence is managed if barriers and setbacks occur. Meanwhile, promoting perceived social support from social environment is critical to prevent relapse (Schwarzer, 2008).

Several studies have confirmed the effectiveness of stage-based interventions based on the HAPA model in improving healthy dietary (Wiedemann, Schüz, Sniehotta, Scholz, & Schwarzer, 2009), physical activity (Lippke et al., 2010), and other health behaviours (e.g., Payaprom, Bennett, Alabaster, & Tantipong, 2011).

[figure not shown]

Figure 1: The Health Action Process Approach (Schwarzer, 2008)

However, it is still uncertain how multiple health behaviours (PA and dietary) can best promote (Vandelanotte et al., 2005). Concepts such as the transfer of learning content from one behaviour field to another (Fleig, Kerschreiter, Schwarzer, Pomp, & Lippke, 2014) or compensatory cognitions (“I have to do some activity now because I have eaten so many candies”) have received little attention (Fleig, Küper, Lippke,

Schwarzer, & Wiedemann, 2015). However, first studies indicate that it is useful to address these concepts explicitly in interventions (e.g., Nigg, Lee, Hubbard, & Min-Sun, 2009).

For the e-health interventions approach (website plus SMS) applied in health behaviour change, in the last decade, a growing body of research has proved its efficacy in diverse populations (e.g., Lustria, Cortese, Noar, & Glueckauf, 2009; Webb, Joseph, Yardley, & Michie, 2010). However, there is a void of e-health interventions for PA and dietary behaviour change among Chinese university students.

Schwarzer R. (2008). Modeling Health Behaviour Change: How to Predict and Modify the Adoption and Maintenance of Health Behaviours. *Applied Psychology: An International Review*, 57: 1–29.

(b) Work done by the investigators (with key references)

During the past several years, the investigators of this study have conducted a series of related research. Targeting Chinese college student samples, [name], the principal investigator, carried out two cross-sectional studies to verify the stage-specific characteristics of PA behaviour change within the HAPA model (Duan, 2006; Duan, Lippke et al., 2011). In addition, [name] conducted two quasi-experimental studies to evaluate intervention effects for PA behaviour promotion among Chinese university students (Duan, Lin & Cui, 2005; Duan, Liu & Wei, 2010).

[name], a co-investigator of this study, has made a large contribution to the field of multiple health behaviour research. In the past, based on the HAPA model, she has successfully and intensively implemented interventions involving motivational and volitional phases of health behaviour change (PA and dietary behaviour) in different settings, such as rehabilitation (e.g., Lippke, Fleig, et al., 2010; Lippke, Fleig, et al., 2015). During April 2012 and March 2015, [name] was involved in an international collaboration project (RENATA), which was managed by [name]. This project was to test the effectiveness of an online field experiment in Germany, Netherland and China to provide an example for the potentials of online applications in health promotion. As one of the research output, the study protocol of RENATA project has been published (Reinwand, Kuhlmann, Wienert, de Vries, & Lippke, 2013). In China, with an internal grant from Hong Kong Baptist University, the PI completed a pilot study of this e-health learning program among Chinese cardiac rehabilitation-aftercare patients in December 2014. This pilot study provided preliminary support in terms of (1) reliability and validity of all Chinese version questionnaires and (2) feasibility of the research methods. All these related research output allows investigators to implement e-health program among Chinese university students to test the intervention effectiveness.

Duan Y.P. (2006). Stage Models of Physical Activity Behavior and Their Application to Chinese Adults (doctoral dissertation). Bayreuth: Bayreuth University Press. Germany.

Three steps will be carried out prior to conducting main study. Step 1: Validating questionnaires and intervention materials in order to match university student population. Researchers first adjust some inappropriate materials, then two students will be asked about their understanding of the questionnaire and intervention materials to ensure the content validity of measurements. Step 2: Setting up a website. Based on the previous e-health study among Chinese cardiac rehabilitation patients, all technological functions of website will be built and implemented. Step 3: Testing website function. Researchers will check all website programs to ensure the operation of website function before launching main study.

(2) Main study stage

On the first PE class in one semester, students will be informed about the study by their lectures with relevant information materials. After making agreement with PE lectures, those students who are willing to participate in and complete this program will get additional 10 marks as bonus in the final PE exam. Once individuals show their interest and consent, they will sign up in a study information sheet and be

required to complete online registration and personal information within the first two weeks (T0). Then students will be randomly assigned into one of three groups. (1) Intervention group I (IG-I): sequentially with PA first (4 weeks) followed by diet (4 weeks); (2) IG-II: sequentially diet first (4 weeks) and then PA (4 weeks); (3) the control group (CG) will not participate in any support program during the intervention period and the 1-month extension. Besides, all groups will be contacted to collect data at the beginning of the intervention (T1), at the end of intervention (T2), and at one month after the intervention (T3). Data collection will be completed on the e-health learning website through electronic questionnaires.

Besides, all groups will be further contacted for collecting data at the beginning of intervention (T1), at the end of intervention (T2), 1 month after the intervention (T3). All data collection will be completed on the e-health website with the use of electronic questionnaires.

Intervention

The intervention will address the basic elements of the HAPA model via the use of behaviour change techniques. In line with Abraham and Michie (2008), we use several behaviour change techniques like providing information about behavioural risk and benefit of behaviour change, prompting intention formation, prompting barrier identification, providing instructions how to perform a behaviour, prompting specific goal setting and review of behavioural goals, providing feedback on performance, prompting practice and providing follow-up prompts, prompting to plan social support and finally prompting relapse prevention, also based on strategies used by other effective computer tailoring programs (Schulz, Kremers, van Osch, Schneider, van Adrichem, de Vries, 2011).

Each of the two intervention groups (IG I-II) will receive an eight-week support program. Participants are required to access the online program once per week and take part in one of the intervention modules. The intervention aims to increase participants' risk perception of cardiovascular diseases, support positive outcome expectancies towards physical activity (PA) and fruit and vegetable intake (FVI), and guide participants in defining and reflecting on their own goals, action plans and coping plans. Further, self-efficacy regarding the participant's ability to perform and maintain the two targeted behaviours will be addressed. Table 1 presents a short overview about the weekly intervention content.

Table1 Intervention content

Weekly sessions	Weekly content
Session 1 PA and Session 5 F&V Session 1 F&V and Session 5 PA	Questionnaire and personalized feedback, increase risk perception and outcome expectations, defining own health outcomes
Session 2 PA and Session 6 F&V Session 2 F&V and Session 6 PA	Personalized feedback, defining action plans
Session 3 PA and Session 7 F&V Session 3 F&V and Session 7 PA	Personalized feedback, evaluation and self-reflection about action plans, adjusting action plans, defining personal barriers, developing personal coping plans, evaluation and reflection about coping plans
Session 4 PA and Session 8 F&V Session 4 F&V and Session 8 PA	Personalized feedback, adjusting coping plans, thinking about social support and development of a list of potential supporters from the social environment (Session 8: T2 questionnaire)

Note: PA stands for physical activity; F&V stands for fruit and vegetable consumption.

The intervention will be enriched by different kinds of feedback: ipsative feedback will be used to provide participants with an overview of their development with regard to PA and FVI (DiClemente, Marinilli, Singh, & Bellino, 2001). At the beginning of each session participants will be asked about PA or FVI during the preceding seven days. After that, they will receive tailored feedback about their behaviour. Normative feedback will be provided to give information about whether the behaviour meets the recommendations for both target behaviours (Schulz, Schneider, de Vries, van Osch, van Nierop, & Kremers, 2012). Feedback will not only be based on the assessment at the beginning of the intervention T1 but also given dynamically with the use of information that will be assessed during the intervention. In this way the feedback is based on the newest information and contains more relevant information. "[name], you ate 3 portions of fruit and vegetable per day. This is a bit more than the last time. Great! But remember, it would be good for you to eat at least 5 portions fruit and vegetable a day. E-health learning program can support you to achieve this goal." In addition, a figure will present the prior behaviour, the behaviour of the past weeks, and whether participants fulfill the recommended amount of PA or FVI.

During the intervention, participants will also simultaneously receive a SMS message via mobile phone each week reminding them of their weekly sessions. SMS reminders will also be sent to participants at T3.

Measures

All measurement instruments have been validated in a previous pilot study with Chinese cardiac rehabilitation participants. Full details of questionnaires are provided in the attachment. The standardized electronic questionnaires consist of four parts.

1. Demographic information: These items include gender, age, study year, university name, marital status, self-reported body height (in cm) and body weight (in kg).

2. Social-cognitive variables related to physical activity and dietary behaviour

Stage algorithm: For PA, participants will be asked "Please think about your typical weeks: Did you engage in PA at least 5 days per week for 30 minutes or more?" Regarding dietary, participants will be asked "Please think about what you have typically consumed during the last weeks: Did you eat five portions of fruit and vegetables per day?" Responses are based on a rating scale with verbal anchors ("No, and I do not intend to start"; "No, but I am considering it"; "No, but I seriously intend to start"; "Yes, but only for a brief period of time"; "Yes, and for a long period of time") and are designed like a rating scale (Lippke, Ziegelmann, Schwarzer, & Velicer, 2009).

Outcome expectancies will be measured by two Pros items and two Cons items for each behavior (Pros: Cronbach's α for PA= 0.76; Cronbach's α for F&V= 0.93. Cons: (Cronbach's α for PA= 0.47; Cronbach's α for F&V= 0.42). (Schwarzer, Lippke, & Luszczynska, 2011). **Self-efficacy:** Self-efficacy will be differentiated into motivational, maintenance and recovery self-efficacies. Motivational self-efficacy will be measured by one item for each behavior. Maintenance self-efficacy will be measured by two items for each behavior (Cronbach's α for PA= 0.64; Cronbach's α for F&V= 0.88). Recovery self-efficacy will be measured by two items for each behavior (Cronbach's α for PA= 0.75; Cronbach's α for F&V= 0.86). (Schwarzer, 2008). **Intention** will be assessed by 3 items for each behaviour (Cronbach's α for PA= 0.34; Cronbach's α for F&V= 0.58). (Lippke et al., 2009). **Risk perception** is adapted from Perloff and Fetzer (1986) and will be measured by 5 items (Cronbach's α = 0.84). **Planning:** Planning will be distinguished into action planning and coping planning. Action planning will be assessed by 3 items for each behavior (Cronbach's α for PA= 0.93; Cronbach's α for F&V= 0.93). Coping planning will be assessed by 3 items for each behavior

(Cronbach's α for PA= 0.92; Cronbach's α for F&V= 0.94). (Schwarzer, 2008). **Perceived social support** will be measured by 3 items for each behavior (Cronbach's α for PA= 0.87; Cronbach's α for F&V= 0.89). (Jackson, Lippke, & Gray, 2011).

3. Past health Behaviour

The level of PA will be measured with the short version of IPAQ questionnaire (Mäder, Martin, Schutz, & Marti 2006). Participants will be asked to estimate the amount of days and spend time for vigorous, moderate and walking activities during the past seven days. To assess the fruit and vegetable consumption during the past seven days, four items will be used. Participants will be asked to count the number of consumed portions or glasses fruit and vegetable a day. It will be distinguished between fruit, fruit/vegetable juice, cooked or steamed vegetable, and raw vegetable (Rafferty, Anderson, McGee, Miller, 2002).

4. Variables related to health

Compensatory health beliefs will be measured by 4 items with Cronbach's α = 0.55. (Knäuper, Rabiau, Cohen, & Patriciu, 2004). **Quality of life:** Respondents will be firstly asked about their general quality of life as "How would you rate your quality of life?", then 7 items in physical health subdomain will be used. (Cronbach's α = 0.89). (WHOQOL-BREF; World Health Organization, 1993).

Statistical analysis:

Data analysis will be performed using SPSS 21.0. Descriptive statistics will be used to describe the baseline characteristics in the study. We will assess whether there are significant differences between the intervention groups compared to the control group according to physical activity and nutrition by means of linear regression analysis in PASW.

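### Random assignment is placed before T1, the self-reported pre-measure, and nothing in the available text keeps the group hidden until T1 is submitted

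*Combined protocol and SAP*

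**What the plan says.** The order of events appears twice and is the same both times. Section 3 (Abstract of research): "The online registration and personal information will be completed within the first two weeks of one semester (T0). Then students will be randomly assigned" to the three groups. Section 6, Procedure, (2) Main study stage: students are "required to complete online registration and personal information within the first two weeks (T0). Then students will be randomly assigned". Once the groups have been described, the Procedure adds that "all groups will be contacted to collect data at the beginning of the intervention (T1), at the end of intervention (T2") and again one month later (T3). Everything is collected by electronic questionnaire on the study website.

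The control group "will not participate in any support program during the intervention period and the 1-month extension".

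The Statistical analysis section names three time points, T1 to T3, and treats the first two as the pre and post measures. It also uses baseline behaviours as MANCOVA covariates. Stage of change is a between-subject factor in the MANOVA and a moderator in the mediation analysis. The section does not say at which wave the covariates or stage are measured.

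Three further passages bear on T1:

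- Table 1 gives the content shared by Sessions 1 and 5 of both intervention arms as "Questionnaire and personalized feedback, increase risk perception and outcome expectations, defining own health outcomes". The row for Sessions 4 and 8 carries the note "Session 8: T2 questionnaire".
- The account of tailoring says: "Feedback will not only be based on the assessment at the beginning of the intervention T1", so T1 answers feed the programme.
- Before allocation, students are told that "those students who are willing to participate in and complete this program will get additional 10 marks as bonus in the final PE exam".

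**The concern.** A pre-measure is unrelated to allocation by design only if allocation, or at least knowledge of it, comes afterwards. Here allocation comes first and the arms are easy to tell apart. A student who learns that a support programme is about to start, or that none is coming, may answer questions on intention, plans or stage differently. That student may also be more or less inclined to fill in T1.

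Two things would then be at stake. First, the reference point for change, and any covariate or stage grouping taken from T1, could itself carry an effect of allocation. Second, the students who have a T1 record might no longer be the three groups as randomised.

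**Working it through.** The plan states no figure on this point, so the check is a reading of the sequence, followed by the algebra of what a disturbed T1 would do.

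1. **Order.** The Abstract and the Procedure agree: T0, then random assignment, then T1.
2. **Content of T0.** It is described only as signing up and giving personal details. No section places behaviour, stage or social-cognitive items there, and the attached questionnaire carries no wave label.
3. **Role of T1.** The analysis runs from T1 to T3, so T1 is the pre-measure and T0 is not an analysed time point. That the baseline behaviours come from T1 is an inference from this. That stage does too is a weaker inference, resting on the stage items being in the same questionnaire.
4. **Disclosure.** The available text does not say when students learn their group, that T1 must be submitted first, or that anyone is blinded.
5. **Completion.** The reminders described are tied to weekly sessions, which controls do not have, and to T3. None is described specifically for T1. The bonus gives every student a reason to finish, but what finishing means for a control is not defined.
6. **Exposure by type of item.** The physical activity and fruit and vegetable items are seven-day recalls and are less open to a change of outlook. Intention, planning and the stage answers that express intent are more open to it.

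**Consequence if the group is known at T1.** Let Δ be the true difference between an intervention arm and control, δ the arm-related shift in T1 answers, δ′ the arm-related shift in later answers, and β the slope on T1 in a covariate-adjusted model. With other things equal:

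- change from T1 estimates Δ + δ′ − δ;
- adjustment for T1 estimates Δ + δ′ − βδ.

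If only T1 shifts (δ′ = 0), the estimate is off by −δ or −βδ. If the same shift persists (δ′ = δ), it cancels in the change score and partly cancels under adjustment when 0 < β < 1. If T1 is completed before disclosure, δ = 0 and both expressions become Δ + δ′. The documents give no value for δ, δ′ or β, so neither size nor direction can be stated.

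**Side check on whether T0 was meant as a measurement.** The stated sample size is 306, for effect size 0.15, alpha 0.05 and power 0.80. Assume the group-by-time test of a repeated-measures MANOVA with k = 3 groups and m measurements, with s = min(m − 1, k − 1), noncentrality N·s·f², and degrees of freedom (k − 1)(m − 1) and s(N − k − (m − 1) + s).

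- m = 4: smallest N is 306 (noncentrality 306 × 2 × 0.0225 = 13.77; df 6 and 604).
- m = 3: smallest N is 268 (noncentrality 268 × 2 × 0.0225 = 12.06; df 4 and 530).

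The stated figure thus fits four measurements, but the plan states neither the test option nor the number of measurements.

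**The case against.** The strongest reply is that the harm needs several conditions that the text does not establish: disclosure before T1, and covariates and stage taken from T1. Measuring a baseline after randomisation does little damage if students do not yet know their group. The document is also a grant form with a page limit, and some of its pages were not available to us. The recruitment materials may deal with disclosure. All of this stands, and it is why the point is put as a risk. It does not alter the stated order, which puts the pre-measure after allocation without an accompanying safeguard.

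A second reply is that 306 fits four measurements, so T0 may have been meant as a pre-allocation baseline. This is only suggestive. The analysis names three time points, and T0 is described as registration.

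A third is that the plan allows for about 30% drop-out and compares drop-outs with finishers. That helps little for loss before T1: those students would have only their T0 details, and the comparison is not said to be made by arm.

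A fourth is that a lasting reporting shift is masked by a T1 taken after disclosure and would show in full once T1 is protected. The algebra bears this out. But it describes a T2/T3 problem, and relying on two biases to cancel is no reason to keep a post-allocation baseline.

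A reader might also infer from Table 1 that T1 is taken inside Session 1, alongside intervention content. The table does not support this. It labels T2 but not T1, the same row covers Session 5, and T1 is due from controls, who have no sessions. It remains an open question.

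**Conclusion.** The point holds as an avoidable weakness in the stated order of steps. Allocation precedes the self-reported pre-measure, the arms are easily distinguished, and the available text does not withhold the group until T1 is in. It is best classed as a cheap improvement.

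Its size and direction are unknown. A reader might conclude that students are told their group before T1, or that the planned comparisons are biased. The documents show neither. The conclusion rests on T1 being the pre-measure, which the analysis section supports directly. Its extension to the behavioural covariates is inferred, and its extension to stage is inferred less firmly.

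**What to change.** Change the stated order in the Abstract and the Procedure to: registration (T0), full T1 questionnaire submitted by every student, random allocation, group revealed, Session 1. If allocation cannot follow T1, the minimum is to withhold the group, and all Session 1 content, until T1 is submitted. State which option applies, say whether the Session 1 questionnaire in Table 1 is T1, and name the wave that supplies the covariates and stage. If that questionnaire is T1, move it to a separate step completed by all three groups; its answers can still drive the tailored feedback.

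Allocating after T1 protects the pre-measure, the baseline covariates and stage from knowledge of the arm, and prevents loss between randomisation and T1. Revealing after T1 gives only the first protection: loss before T1 could still occur, but would not be driven by knowing the arm. Neither option touches arm-related self-reporting at T2 and T3, which should be written in as a limitation.

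The questionnaire itself need not change. The Research Schedule puts website set-up and testing in Months 1-9 and the main study in Months 10-13, so the order can be set before launch. The documents do not describe how allocation is carried out, so the small cost assumes that this step can be made to follow T1 when the site is built. The other downside is that students who do not complete T1 are not randomised, which may narrow the sample slightly.
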